In this aim, we will conduct a pilot randomized controlled trial of patients with asthma or parents of children with asthma who lost employer-sponsored coverage during the COVID-19 pandemic. Potential study subjects will be recruited through AAFA and HPHC. Eligible participants will be randomized into one of two study groups: 1) an intervention group that receives access to an asthma chat bot and personalized insurance navigation (n=145), or 2) a wait-list control group (n=285). At study entry, participants will receive an online baseline survey to assess outcomes related to insurance coverage, asthma severity and control, medication use and adherence, asthma care access and affordability, and COVID-19 related illness. The intervention group will be offered the chat bot and AAFA navigation services. Navigation will be provided through AAFA's existing online patient community platform that provides assistance with clinical, educational and financial questions and includes secure, personal messaging capabilities that will be supplemented with telephonic outreach. One month later, we will field a follow-up survey to measure short-term changes in outcomes; for the intervention group, this survey will also measure implementation outcomes including uptake, feasibility, acceptability, and usability. Four months later, we will field a second follow-up survey to measure longer-term changes in outcomes. Control subjects will be offered the chat bot after completion of the follow-up surveys. If findings suggest that the intervention is feasible and effective, we will use effect sizes from this pilot to power a larger comparative effectiveness trial in the future.

Participants

Eligible subjects will include adults aged 18-64 years who have asthma or have a child with asthma aged 4-17 years, and lost employer-sponsored health insurance after February 2020. Only one person per household will be eligible. Potential subjects will be recruited through AAFA, who will send out a description of the study to potential subjects through its online community, email listserv, website, Facebook page, and newsletter, and through its partner hospital programs and Medical Scientific Council (PC-2). Potential subjects will also be recruited through HPHC. Members who

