Four months later, intervention and control subjects will be emailed a RedCap link to a similar followup survey to measure changes in insurance coverage, asthma care and control, health care access, and affordability. The survey will be designed to be completed in an average of 20 minutes and we will offer a \$20 gift card for completion. We will attempt to contact non-responders by telephone to encourage them to complete the surveys (MD-1). Survey subjects will be asked for permission to be contacted again for participation in a telephone interview for Aim 2.

Outcomes

Outcomes include patient-centered, patient-reported outcomes that people with asthma have raised as concerns in our prior qualitative work in the parent project and that have been identified as meaningful in the parent AFFORD project by our stakeholder partners from AAFA, the Patient Family Advisory Council, and the AFFORD Advisory Board (RQ-6, PC-1, PC-3). The primary outcome will be whether the participant with asthma (or their child with asthma) has insurance coverage. Secondary outcomes will include whether the person with asthma used less asthma medication than prescribed because of cost, and whether they experienced health care-related financial burden (problems paying medical bills and/or paying off medical bills over time, having to set up a payment plan with a doctor or hospital, having trouble paying for other basic bills like food, heat, or rent because of medical costs). Other outcomes will assess asthma care use, asthma control using the Asthma Control Test (ACT), health status, mental health/worry, and material hardships such as food or housing insecurity. These include validated measures and measures used in prior surveys by the study team and others (IR-4).²⁶⁻³³

Analysis Plan (IR-3)

We hypothesize that participants receiving the intervention will be more likely to have coverage at four-month follow up (primary outcome) and will be less likely to report non-adherence to asthma medications, delayed/forgone asthma care, and financial burden than those receiving usual care (secondary outcomes).

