We will compare unadjusted outcomes between the intervention and control groups using chi square and t tests; because of the randomized study design this difference measures the causal impact of the intervention. We will conduct post hoc exploratory analysis to assess differences in intervention effectiveness by race/ethnicity to assess whether the intervention reduces racial/ethnic coverage disparities (RQ-4; HT-1). Given the small pilot nature of this study, these analyses will be hypothesisgenerating rather than hypothesis-testing (HT-2-4). The survey will measure important co-variates such as age, gender, income, race/ethnicity, education, state of residence, asthma severity, and family composition, and analyses will adjust for any co-variates that are not balanced between study groups (IR-1). In this pilot study, efficacy testing will be limited but we expect to have 100 intervention and 200 control subjects with follow-up data to be able to detect absolute differences of 10% or more between study groups in changes in uninsurance rates with 80% power with a two-tailed alpha of 0.05. We assume 30% loss to follow-up from baseline to four-month follow-up. Given the small pilot nature of this study, we will track dropout carefully in order to inform feasibility assessment and planning for a larger trial. We will closely monitor timing of dropout, impact of strategies such as telephone outreach, and characteristics of those dropping out compared to those retained, and will use multiple imputation methods to conduct a sensitivity analysis to test the sensitivity of findings analyzed with and without imputed data (MD-2-5). Findings will be reported using CONSORT reporting guidelines (IR-6).

Patient stakeholders from the AFFORD Patient Family Advisory Council will provide input on interpretation of study findings in the context of their lived experience, and will provide input on strategies for dissemination to key stakeholders (PC-1, PC-4).

Aim 2:

Overview

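### The primary four-month coverage result is a responder-only comparison read as causal; it leaves one-month coverage answers unused and is biased if dropout depends on them differently in the two arms

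*Combined protocol and SAP*

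**What the plan says.** The primary outcome is whether the person with asthma has insurance coverage, tested at four months (Aim 1, Outcomes and Analysis Plan). The main analysis reads "We will compare unadjusted outcomes between the intervention and control groups using chi square and t tests", and the plan adds that "because of the randomized study design this difference measures the causal impact of the intervention".

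The Overview and Design sections give 145 participants in the intervention arm and 285 in the wait-list arm. On missing data, the Analysis Plan says "We assume 30% loss to follow-up from baseline to four-month follow-up" and "we expect to have 100 intervention and 200 control subjects with follow-up data". It monitors when people drop out, compares those lost with those retained, and runs multiple imputation as a sensitivity analysis, with results shown with and without imputed values. Non-responders are telephoned (Data collection).

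Coverage is also asked earlier: "One month later, we will field a follow-up survey to measure short-term changes in outcomes" (Overview).

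The plan does not say which variables enter the imputation, whether it is run by arm, or how disagreement between the two results would be read. The only adjustment is for unbalanced covariates, and one-month coverage is not among those listed.

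**The concern.** The plan never uses the words complete-case, but the sample is described as people with follow-up data and imputation is reserved for sensitivity. The natural reading is that the headline four-month result uses responders only. Someone who answers at month one and is lost by month four then adds nothing, although their one-month coverage is likely to be the best available predictor of the missing answer.

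Randomisation protects the comparison of everyone randomised. It does not by itself protect a comparison of the roughly 70% who answer. Only the intervention arm is offered navigation before the follow-up surveys, so the relation between being insured and continuing to respond could differ by arm. For example, people whom navigation did not help may stop answering.

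The plan aims to "detect absolute differences of 10% or more between study groups in changes in uninsurance rates", and the Overview says that effect sizes from this pilot will power a larger trial if the findings are favourable. A shift of a few points would be sizeable against a 10-point target and would carry into that next design.

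**Working it through.** **The plan's own figure.** 145 × 0.70 = 101.5 and 285 × 0.70 = 199.5, which agrees with the stated 100 and 200. About 300 of 430 people would be analysed.

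**Assumed inputs.** The documents give no coverage rates and no split of dropout by time or arm, so everything in this paragraph is an assumption. At month one, 35% are uninsured. At month four, 72% of those uninsured at month one and 8.5% of those insured at month one are uninsured. There is no true effect, and control-arm dropout is unrelated to coverage. About 30% are lost overall in each arm.

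**Formula.** Let p be the share uninsured at month one, and d_U and d_I the later loss among the uninsured and the insured in the intervention arm. Among responders the share becomes p_R = p(1 − d_U) / [p(1 − d_U) + (1 − p)(1 − d_I)]. The responder difference shifts in favour of the intervention by (p − p_R) × (0.72 − 0.085) = (p − p_R) × 0.635.

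**Link in the intervention arm only, after month one.**
- 25% v 14% lost: p_R = 0.2625 / (0.2625 + 0.5590) = 0.3195. Shift = 0.0305 × 0.635 = 1.9 points.
- 30% v 11%: p_R = 0.2450 / (0.2450 + 0.5785) = 0.2975. Shift = 0.0525 × 0.635 = 3.3 points.
- 42% v 19%: p_R = 0.2030 / (0.2030 + 0.5265) = 0.2783. Shift = 0.0717 × 0.635 = 4.6 points.

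The first two cases put a 15% loss, unrelated to coverage, before month one. Overall retention in the second is 0.85 × 0.8235 = 0.70. The third puts most loss after month one.

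**Type I error by simulation, 145 v 285.** An unpooled Wald test gives about 7%, 10% and 14% in the three cases. A pooled chi-square without continuity correction gives 6.3%, 8.5% and 12.7%. The nominal level is 5%. Standardising month-four coverage over one-month coverage within each arm brings the shift to about 0 in all three. The standard deviation of the estimate is 5.4 to 5.5 points with either method.

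**Same link in both arms.** With no true effect the shift is about 0; individual simulations gave 0.0 to 0.3 points. Under a second assumed set (month-four coverage 90% if covered at month one and 30% if not, 60% of controls covered at month one, 70% retained, covered people 20 points more likely to respond), a true 10-point difference is underestimated by 1.0 point.

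**Loss before month one that also depends on coverage.** Take the 30% v 11% case and let early intervention-arm loss be 26% of the uninsured and 9% of the insured.
- Share uninsured among month-one responders: 0.2590 / (0.2590 + 0.5915) = 0.3045.
- After the later loss: (0.3045 × 0.70) / (0.3045 × 0.70 + 0.6955 × 0.89) = 0.2562.
- Total shift: (0.35 − 0.2562) × 0.635 = 6.0 points.
- Left after standardising on one-month coverage: (0.35 − 0.3045) × 0.635 = 2.9 points.

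The second assumed set shows the same pattern when the 20-point gap is in the intervention arm only. Covered share among responders is 0.6 × 0.78 / 0.70 = 0.6686, so the shift is 0.0686 × 0.60 = 4.1 points. By simulation, using one-month coverage leaves 0.0 points if all loss falls after month one and 1.6 if half falls before. If all of it falls before, nothing is corrected.

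**The case against.** The plan does not ignore dropout. It tracks timing and characteristics, telephones non-responders and commits to multiple imputation. If one-month coverage were in that imputation, the comparison with and without imputed data would reveal the shift. On this view the gap is an unspecified model, and exchanging the primary and sensitivity labels changes little. In a pilot where efficacy testing is said to be limited, a simple test is a defensible headline, and precision hardly changes (SD 5.16 v 5.31 points when dropout is unrelated to coverage).

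Much of this stands. The planned imputation could do the job, and the gain is in bias rather than precision. But the plan does not commit the imputation to one-month coverage or to separate models by arm, and it does not say which result prevails if they disagree. Its causal statement attaches to the unadjusted difference. Choosing the headline is therefore more than a label.

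A reader might also infer that any dropout linked to one-month coverage biases the result. The documents do not support that: a link shared by both arms leaves 0 to about 1 point, and nothing in them shows a link that differs by arm. Nor do they support the inference that the one-month data would largely repair the problem. The 30% loss runs from baseline with no split in time, and anyone lost before month one has no one-month answer to use.

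**Conclusion.** The concern holds conditionally. The primary comparison is in effect responder-only, it does not use one-month coverage, and randomisation alone does not justify its causal description with 30% expected to be missing. If the dropout link differs by arm, the bias is about 2 to 4.6 points and type I error about 7% to 14% (about 6% to 13% with a pooled chi-square). If the link is shared, the bias is about 0 to 1 point. All of these figures rest on assumed coverage and response rates.

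Using one-month coverage removes the part of the bias that arises after month one and depends on that answer. It does not correct coverage-linked loss before month one (2.9 of 6.0 points remain in the scenario shown) or dropout that depends on unseen month-four coverage. Links running in opposite directions in the two arms would give a larger shift, 8.3 points under the second assumed set, but nothing in the documents points to that.

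This is worth changing before analysis. It is not evidence that the pilot's result will be wrong.

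**What to change.** In the Aim 1 Analysis Plan:
- Take the primary four-month risk difference and its 95% CI from the multiple imputation already planned, run separately by arm with baseline and one-month coverage in the model. An equivalent longitudinal model for the binary outcome would also serve.
- Use one-month coverage to predict missing month-four answers, not as an ordinary adjustment covariate. It is measured after the intervention starts, and adjusting for it could remove part of the effect.
- Keep the responder-only chi-square as the sensitivity analysis, and state how a disagreement will be read.
- Drop the claim that the responder difference is causal on randomisation alone. Report loss by arm, before and after month one, and by one-month coverage where known.
- State that dropout depending on unseen month-four coverage is not covered by this change and needs its own sensitivity analysis.

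The cost is SAP wording and a little more analysis, with no new data or participants. The small downside is that the headline depends on an imputation model; the retained responder-only result makes that dependence visible.

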disenrolled from employer-sponsored plans after February 2020 will be identified, and those aged 4-64 with an ICD-10 diagnosis code for asthma in claims data after January 1, 2019 will be contacted by email and invited to participate. Recruitment materials will include a description of the study and a RedCap survey link which will ask screening questions to determine eligibility. Any participant suspected of being duplicative or fraudulent will be ineligible for the study and removed. We will collect information on race/ethnicity and select a sample representative of the racial/ethnic distribution of patients with asthma, with no more than 60% non-Hispanic White selected for the sample (PC-2). The estimated racial/ethnic and gender of the study population is described in Table 1.

Race	Male (N)	Female (N)	Total (N)				
American Indian/Alaska Native	0	0	0				
Asian	0	0	0				
Black/African American	19	96	115				
Hawaiian/Pacific Islander	0	0	0				
White	76	201	277				
Multirace	19	19	38				
Ethnicity	Male (N)	Female (N)	Total (N)				
Hispanic (Latino/Latina)	10	19	29				
Non-Hispanic	104	297	401				

Table 1. Estimated Racial/Ethnic and Gender Enrollment

Design

We will conduct a pilot randomized controlled trial where we will randomize participants who lost coverage to: 1) be offered a combination of automated chat bot and personalized outreach provided by AAFA-affiliated navigators (n=145), or 2) be a wait-list control (n=285). We will use a wait-list, usual care control group as the comparator given that there is no other standard treatment or practice for people with asthma who lose insurance coverage to which to compare our navigation intervention (RQ-5). A diagram of the study flow can be found in Figure 1. After randomization, participants will be given a RedCap link for a baseline survey. REDCap is a HIPAA secure web-application that the Harvard Pilgrim IRB has approved for securely collecting survey data via email which allows study subjects to enter data directly into a form that is then transmitted securely to the Harvard Pilgrim server. The survey instrument will contain structured, closed-ended questions designed to be completed in an average of 20 minutes. The survey will assess past and current insurance coverage, asthma severity and control, medication use and adherence, other asthma care use, current access and cost challenges, and COVID-19 related illness. We will offer a \$20 gift card for completion of the survey.

Intervention

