After completion of the baseline survey, intervention subjects will be sent an email with information about AAFA's asthma chat bot and a link to access it and information about AAFA's insurance navigation program, how it can help with finding coverage and managing asthma costs, and how to access it via group and private messaging within AAFA's asthma community platform with the availability of telephonic follow-up from AAFA navigators. Subjects can access AAFA's community

platform through a password-protected account, through which they can join the private group where they can ask questions and share resources, with moderation by AAFA staff. They will be able to send a "group private message" that includes the subject, the AAFA staff providing navigation support, and the AAFA administrator. Subjects will then communicate with AAFA staff about insurance issues, access to asthma care, and assistance with asthma costs. Messages are referred

Figure 1: Study flow

to trained AAFA staff who respond by the next business day—and usually within the same day— with answers, referrals, or other follow-up. AAFA's online community is staffed with trained community engagement managers during "normal" business hours as well as nights and weekends in order to be available for patients when they need support. For subjects in this study, AAFA staff will offer telephonic follow-up as needed to help identify available insurance options and eligibility criteria and suggest important insurance plan attributes and cost management strategies to consider.

Data collection

One month after receiving the intervention, subjects will be emailed a RedCap link to a follow-up survey to measure changes in insurance coverage and other outcomes. The follow-up survey will be structured similarly to the baseline survey, with closed-ended questions about insurance coverage, asthma care and control, health care access and affordability. For intervention subjects, the follow-up survey will also ask closed and open-ended questions about implementation outcomes such as uptake, acceptability, feasibility, usability, and fidelity. The survey will be designed to be completed in an average of 20 minutes and we will offer a \$20 gift card for completion.

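### Adjustment for baseline asthma control is not prespecified although it is collected, so the Asthma Control Test comparison gives up precision

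*Combined protocol and SAP*

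**What the plan says.** **Analysis.** The Analysis Plan (IR-3) under Aim 1 gives the between-group comparison as "We will compare unadjusted outcomes between the intervention and control groups using chi square and t tests". Later in the same paragraph it says that "analyses will adjust for any co-variates that are not balanced between study groups". The covariates it names as examples are "age, gender, income, race/ethnicity, education, state of residence, asthma severity, and family composition". It gives no threshold for imbalance and no model.

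**Baseline.** According to the Aim 1 Overview, "participants will receive an online baseline survey to assess outcomes related to insurance coverage, asthma severity and control". The Design section agrees: "The survey will assess past and current insurance coverage, asthma severity and control, medication use and adherence".

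**Follow-up.** Of the one-month survey, Data collection says: "The follow-up survey will be structured similarly to the baseline survey". The four-month instrument is described as a similar "survey to measure changes in insurance coverage, asthma care and control, health care access, and affordability".

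**Rank of the outcome.** The Outcomes section places "asthma control using the Asthma Control Test (ACT), health status, mental health/worry" among the other outcomes, below the primary outcome (coverage) and the secondary outcomes (cost-related underuse of medication, and financial burden).

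**Timing.** Under Design, the baseline survey link is sent after randomization. Under Intervention, the intervention email goes out once that survey is completed.

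**The concern.** A person's earlier score on a scale usually predicts the later score on it. When both are collected, a comparison that conditions on the earlier score has a smaller standard error and is protected against a chance difference in baseline control between the arms. The plan collects the baseline measure of asthma control but does not commit to using it in this way.

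What is at stake is the width of the interval for the ACT difference. The plan itself says that efficacy testing will be limited, and the Overview says that effect sizes from the pilot will be used to power a larger trial if findings are favourable. An avoidably noisy estimate is less useful for that purpose.

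**Working it through.** **Inputs from the documents.** 145 and 285 randomized; 30% loss; 100 and 200 with follow-up data; two-sided alpha 0.05; 80% power.

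**Inputs assumed.** The ACT is analysed as a score. Its correlation r between baseline and follow-up is 0.3 to 0.7. Its SD is the same at both times (needed for the change-score column).

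**The plan's own figures.** 145 × 0.7 = 101.5 and 285 × 0.7 = 199.5, which agree with the stated 100 and 200. The stated 80% power concerns a 10-point difference in uninsurance. It cannot be checked without a base rate, and nothing below depends on it.

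**Formulas, in SD units.**
- Standard error (SE), unadjusted: sqrt(1/100 + 1/200) = 0.1225
- Detectable difference, unadjusted: (1.96 + 0.84) × 0.1225 = 0.343
- ANCOVA: 0.343 × sqrt(1 − r²)
- Change score: 0.343 × sqrt(2(1 − r))
- Effective total with ANCOVA: 300/(1 − r²)
- Power at a true 0.30 SD: Phi(0.30/SE − 1.96), which is 69% unadjusted

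| r (assumed) | Unadjusted | Change score | ANCOVA | Effective total, ANCOVA | Power at 0.30 SD, ANCOVA |
|---|---|---|---|---|---|
| 0.3 | 0.343 | 0.406 | 0.327 | 330 | 73% |
| 0.5 | 0.343 | 0.343 | 0.297 | 400 | 81% |
| 0.6 | 0.343 | 0.307 | 0.274 | 469 | 87% |
| 0.7 | 0.343 | 0.266 | 0.245 | 588 | 93% |

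The variance of the change-score contrast divided by that of ANCOVA is 2(1 − r)/(1 − r²) = 2/(1 + r). This exceeds 1 for every r below 1, so ANCOVA is the more precise of the two throughout, but by less as r rises.

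**Does the imbalance rule make up the difference?** Suppose that baseline ACT counts as a covariate and that imbalance means a baseline p value below 0.05 (an assumption, since the plan sets no criterion). In 20,000 simulated trials per correlation, with 100 and 200 subjects and no true effect:

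| r | SE, unadjusted | SE, adjust only if imbalanced | SE, always ANCOVA | Share of gain recovered | Type I error under the rule |
|---|---|---|---|---|---|
| 0.3 | 0.1227 | 0.1211 | 0.1170 | 0.0016/0.0057 = 28% | 4.9% |
| 0.5 | 0.1221 | 0.1177 | 0.1059 | 0.0044/0.0162 = 27% | 4.3% |
| 0.7 | 0.1229 | 0.1141 | 0.0878 | 0.0088/0.0351 = 25% | 3.5% |

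The unadjusted test rejected in 5.2%, 5.0% and 5.0% of all null trials, so it is valid overall. In the null trials where the baseline score happened to be significantly imbalanced, it rejected in 11%, 17% and 34%.

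**The case against.** Four stronger readings are tempting, and the documents do not support any of them.

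1. **That the plan compares follow-up scores and ignores baseline.** The text does not say whether follow-up values or changes are compared. The surveys are described as measuring changes, and the power statement is framed in changes in uninsurance. If change scores are meant, the baseline is used and the gain from ANCOVA is smaller at the higher correlations: 0.266 against 0.245 SD at r = 0.7.
2. **That the imbalance rule shuts out baseline ACT.** The covariate list is introduced as examples, and the rule covers any unbalanced covariate. Baseline asthma control could come in. What stands is that nothing commits the analyst to it, the trigger is undefined and depends on the data, and smaller chance differences would stay in the result.
3. **That every score outcome is affected.** Health status and worry are not described as scores, and neither appears in the stated content of the baseline survey. Only the ACT is a named scale, and its analysis by t test rather than as a category is itself an inference.
4. **That the unadjusted test is biased, or that chance baseline differences are a further harm on top of lost precision.** Over randomization the test is unbiased with correct type I error. The chance baseline difference, with a standard deviation of 0.12 SD, contributes to variance already reflected in the t-test interval.

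Two further objections limit the weight of the point. The gain depends wholly on an assumed correlation, and at r = 0.3 it is small. The ACT is also absent from the stated hypotheses, and the sample size rests on coverage. Both stand and lower the priority, but neither is a reason to leave a collected baseline value out of the model.

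**Conclusion.** The point holds as one of efficiency for the ACT. The plan does not prespecify adjustment for a baseline measure that it collects. Relative to an unadjusted t test, ANCOVA would cut the variance by r²: 9%, 25%, 36% or 49% at r = 0.3, 0.5, 0.6 or 0.7. Relative to a change-score t test, the detectable difference falls from 0.406 to 0.327, 0.343 to 0.297, 0.307 to 0.274, or 0.266 to 0.245 SD at the same correlations. The conclusion rests on the ACT being scored at both times and on a correlation that the documents do not give; its direction is the same across the whole range. Priority is low to moderate.

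**What to change.** In the Analysis Plan (IR-3) under Aim 1:

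- State that the main analysis of the ACT is a linear model of the follow-up score on arm and the same score at baseline, fitted regardless of observed balance. Report the adjusted mean difference with a 95% interval, and give the unadjusted difference as support.
- Apply the same model to any other outcome that is in fact scored on the same scale at both times.
- Add a term for adult or childhood form if both are used (a childhood form of the test is among the cited instruments).
- Because the baseline survey follows randomization, specify that the baseline value is the one given before the intervention email, and state whether participants knew their allocation when they completed it.
- Say how a missing baseline score is handled, for example by imputation or a missing indicator.

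The cost is a few sentences of analysis wording. No new data, visits or participants are needed.

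### Baseline coverage is not fixed as a covariate, adjustment depends on an undefined imbalance, and no result is labelled primary: a cheap gain in precision and pre-specification

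*Combined protocol and SAP*

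**What the plan says.** The Analysis Plan (IR-3) under Aim 1 hypothesises that intervention participants will be "more likely to have coverage at four-month follow up (primary outcome"), so outcome and time point are fixed. The stated comparison is unadjusted: "We will compare unadjusted outcomes between the intervention and control groups using chi square and t tests". After naming eight example covariates in an open list, which does not include baseline coverage, it adds that "analyses will adjust for any co-variates that are not balanced between study groups (IR-1"). It gives no test or threshold for imbalance, no model, and no word on whether the unadjusted or the adjusted result is primary. The power sentence uses different language again, aiming to "detect absolute differences of 10% or more between study groups in changes in uninsurance rates".

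Coverage at entry is measured. Under Design: "The survey will assess past and current insurance coverage, asthma severity and control, medication use and adherence". The timing is also given there: "After randomization, participants will be given a RedCap link for a baseline survey". The Intervention section sends the intervention email after that survey is completed. Entry coverage need not be the same for everyone. Under Participants, adults qualify if they have asthma or a child with asthma "and lost employer-sponsored health insurance after February 2020", and health-plan members are approached if they "disenrolled from employer-sponsored plans after February 2020 will be identified". Neither condition requires being uninsured at enrolment.

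**The concern.** Whether a covariate happens to differ between randomised arms says little about whether adjusting for it is worthwhile. That depends on how well it predicts the outcome. Current coverage is a plausible strong predictor of coverage four months later, but under this rule it would be used, at most, when it happened to look imbalanced.

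Two things are at stake. The first is precision. The Aim 1 Overview says that, if findings are favourable, the pilot's effect sizes will be used to power a larger trial, so a tighter estimate has value even where efficacy testing is acknowledged to be limited. The second is pre-specification. With an unadjusted and a possibly adjusted result both planned, no criterion for moving between them and no primary label, the choice could be made after seeing the data.

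**Working it through.** **The plan's own figures.** With 30% loss, 145 × 0.70 = 101.5 and 285 × 0.70 = 199.5, which agrees with 100 and 200 analysed. The 80% power figure cannot be reproduced, because no uninsurance rate is given. For a two-proportion test, power = Φ[(Δ − 1.96·SE₀)/SE₁]. At 20% v 10% uninsured:
- pooled rate = (0.10 × 100 + 0.20 × 200)/300 = 0.167
- SE₀ = √(0.167 × 0.833 × 0.015) = 0.0456
- SE₁ = √(0.10 × 0.90/100 + 0.20 × 0.80/200) = 0.0412
- power = Φ(0.26) = 60%

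The same formula gives 79.5% at 14% v 4%, 45% at 30% v 20% and 37% at 50% v 40%.

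**Assumed setting** (none of these rates is in the documents). A share u is uninsured at baseline. Of control participants uninsured at baseline, 60% remain so at four months (persistence). Of those insured at baseline, 5% are uninsured at four months (lapse). The 10-point effect arises among the baseline-uninsured, whose intervention rate is therefore 0.60 − 0.10/u. There are 100 v 200 participants and 40,000 simulated trials per column. Fixed adjustment is standardisation: arm rates within baseline-coverage groups, averaged over all participants, with an unpooled SE. The conditional rule uses the chi-square unless baseline coverage is imbalanced, and then the standardised result. Two imbalance criteria are tried, both assumptions: p<0.05 (met in about 5% of trials) and standardised difference >0.1 (met in 41–44%).

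| Uninsured at baseline | 30% | 50% | 70% | 90% | 95% |
|---|---|---|---|---|---|
| Power, chi-square | 58 | 44 | 39 | 38 | 39 |
| Power, unadjusted, unpooled SE | 64 | 47 | 40 | 39 | 39 |
| Power, fixed adjustment | 71 | 57 | 47 | 40 | 38–40 |
| Gain with same SE type (points) | 8 | 10 | 7 | 2 | about 0 |
| Variance ratio, fixed adjustment | 0.82 | 0.77 | 0.82 | 0.92 | 0.96 |
| Power, rule at p<0.05 | 59 | 44 | 39 | 38 | 38 |
| Variance ratio, rule at p<0.05 | 0.95 | 0.93 | 0.95 | 0.98 | 0.99 |
| Power gain over chi-square, rule at std. diff. >0.1 | 6 | 5 | 3 | 1 | 1 |
| Variance ratio, rule at std. diff. >0.1 | 0.84 | 0.79 | 0.84 | 0.93 | 0.96 |

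Repeat simulations agree within about 1.5 points. The raw gap between chi-square and fixed adjustment at 30% (58 to 71) overstates the benefit of adjustment, since about 6 points come from the SE type.

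**Worked case, u = 50%.** Four-month uninsurance is 0.5 × 0.40 + 0.5 × 0.05 = 22.5% (intervention) and 0.5 × 0.60 + 0.5 × 0.05 = 32.5% (control). Unadjusted SE = √(0.225 × 0.775/100 + 0.325 × 0.675/200) = 0.0533, a 95% half-width of 10.4 points. Multiplying by √0.77 gives 9.2.

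**Imbalance that escapes the rule, u = 50%.** At p<0.05 it is up to 1.96 × √(0.5 × 0.5 × 0.015) = 12.0 points. The baseline slopes are 0.40 − 0.05 = 0.35 (intervention) and 0.60 − 0.05 = 0.55 (control), so the shift in the estimate is 12.0 × (0.35 × 2/3 + 0.55 × 1/3) = 5.0 points. At standardised difference >0.1 it is about 0.1 × 0.5 = 5 points of imbalance and 5 × 0.417 = 2.1 points of shift.

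**Sensitivity.** With 40% persistence the same-SE gain is about 1/3/3/1 points and the variance reduction 4/8/8/3% at 30/50/70/90% uninsured.

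**Type I error.** Chi-square is about 5%, fixed adjustment about 5 to 6%, the rule at p<0.05 about 4 to 5%, and the rule at standardised difference >0.1 roughly 3 to 5%. Rejecting if either the chi-square or the adjusted test is significant gives about 6 to 9%.

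**The case against.** The strongest reply is that nothing here is wrong. Under randomisation the unadjusted comparison is unbiased, it comes first in the plan, and the plan itself says that this difference measures the causal effect. Only the word primary is missing, in a pilot that concedes limited efficacy testing. That stands, and it limits the point to an improvement. A reader might infer that the conditional rule biases the result or inflates type I error; applied mechanically it does neither, and is if anything conservative. Inflation arises only if the choice of result is left open.

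A reader might also infer that the conditional rule recovers almost no precision. That holds only for a p<0.05 criterion, which the plan does not state. With a standardised difference above 0.1, most of the variance gain is captured. Power rises less than the variance suggests, because trials that do not meet the criterion still use the wider unadjusted standard error.

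Nor does the 5-point shift describe a typical trial. It averages zero over trials, and even with a p<0.05 criterion a difference of more than 5 points between the two estimates occurs in about 1% of the trials left unadjusted at 50–70% uninsured.

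The gain could be near nil. The intervention aims to help people regain coverage, so a mostly uninsured sample is possible. This stands.

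Finally, the wording about changes in uninsurance might signal an analysis that uses baseline. It might, but no change-score or baseline-adjusted model is specified, and the wording does not match the four-month endpoint.

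**Conclusion.** The point holds as a cheap improvement in precision and pre-specification, somewhere between optional and recommended. The textual part is firm: there is no imbalance criterion, no model, no primary label, and baseline coverage is not fixed as a covariate. The numerical part rests on assumed rates. The variance reduction is about 4 to 23% at 60% persistence and 3 to 8% at 40%. The same-SE power gain runs from nil when nearly everyone is uninsured at entry to about 10 points at an even mix. In every scenario run, fixed adjustment did about as well as or better than the conditional rule under either criterion, with type I error close to nominal.

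A reader might conclude that adjustment would restore the stated 80% power. The calculations do not support that: in the main scenarios the adjusted analysis reaches at most about 72%.

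**What to change.** In the Aim 1 Analysis Plan, name one primary analysis: the between-arm difference in the proportion covered at four months, with 95% CI, adjusted for baseline coverage whatever the observed balance, by standardisation or a model with robust standard errors. Delete the adjust-if-unbalanced rule, tabulate balance descriptively, and keep the unadjusted chi-square as supportive. Reword the power sentence to refer to the four-month outcome.

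Three details need stating:
- Baseline coverage is the status reported before the intervention email.
- Missing baseline values are kept as a not-reported category, with counts by arm. With 10% missing at random, adjusted power in the main scenarios is 70/55/46/40/38%; missingness that depends on arm was not examined.
- A numerical sparse-cell rule, fixed in advance and assessed on baseline data without outcomes, governs reverting to the unadjusted result. At 95% uninsured, the 100-person arm has fewer than 2 insured people in about 4% of trials (0.95¹⁰⁰ + 100 × 0.05 × 0.95⁹⁹ = 0.037).

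The cost is wording, settled before four-month outcomes are compared by arm; no new data or participants are needed. The downside is that baseline coverage is self-reported after randomisation, and the documents do not say whether participants know their arm when they answer. The unadjusted test avoids that dependence, which is a reason to keep reporting it.
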